7. STATISTICAL DESIGN

7.1 EVALUABILITY

All subjects who receive study medication will be evaluable for the safety analysis. All subjects who are randomized to receive study medication will be evaluable for the intent-to-treat analysis.

Unless specified otherwise, SPSS® Version 10.0 or higher will be utilized to perform the statistical analyses of efficacy and safety measures.

Categorical variables will be summarized in general using frequencies and percentages, whereas continuous variables will be summarized in general using descriptive statistics of number of observations (n), mean, standard deviation (SD), minimum (Min), median, and maximum (Max).

Hypothesis testing, unless otherwise indicated, will be performed at the 5% significance level. All P values will be rounded to four decimal places; P values less than 0.0001 will be presented as '<0.0001' in all tables. All group comparisons from analysis of variance (ANOVA) and/or analysis of covariance (ANCOVA) models will be based on Type III sums of squares. All confidence intervals will be two-sided with 95% coverage.

Missing or invalid data of efficacy assessments will be handled by individual scales or subscales on the basis of each individual assessment. Missing data for individual items will be assessed for each assessment of each scale and imputed with the mean score of the corresponding assessment and rounded up to the nearest integer if the number of items with missing data or invalid is less than or equal to 20% of total item number. Otherwise, the assessment score will be set to missing.

Considering that a subject's burn wound may be healed and/or a subject may discontinue from the study prior to the end of the study period, missing values at each weekly visit due to either burn wound healing or early termination or any other reasons will be imputed in this study prior to deriving the efficacy endpoints for evaluation, using the technique of last-observation carried forward (LOCF). By so doing, a burn wound that heals sooner will be given more weight for efficacy.

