7.1.2 Secondary Efficacy

The secondary efficacy endpoint is to evaluate the effect of daily Collagenase Santyl ointment versus daily Bacitracin ointment on scar appearance at 90 days and at 180 days after the initiation of treatment. The secondary efficacy endpoint is defined as the VSS total score obtained at Visit 7 (Day 90) and at Visit 8 (Day 180).

The treatment effect of Collagenase Santyl ointment versus Bacitracin ointment on the VSS total scores will be obtained at each of the two post-healing assessment time points, using analysis of variance (ANOVA) for the ITT population. The mixed-effect model will utilize SPSSPROC MIXED to perform the analysis and define treatment (Santyl vs. Bacitracin) and assessment time point (4 visits: Visits 5, 6, 7 and 8) as well as their interaction as fixed effects, and subject as a random effect. The option of variance components will be used to define the covariance structure of the model.

In addition, a model-based t-test comparisons between Santyl vs. Bacitracin will be performed for each of the 2 assessment time points (or visits).

The null hypothesis states that there are no differences between the two treatments, with the alternative of non-zero differences. The type I error rate for rejecting a null hypothesis will be set at an alpha level of 0.05.

Prior to conducting the analysis, those VSS total scores that are obtained at the early termination visit will be assigned to the next scheduled study visit.

The analyses of the primary efficacy evaluations will also be performed for the PP population.

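### The VSS mixed model in 7.1.2 forces one variance on every visit it includes, so the Day 90 and Day 180 tests and intervals are miscalibrated if scar-score spread differs between visits

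*Combined protocol and SAP*

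**What the plan says.** Section 7.1.2 sets the endpoint: "The secondary efficacy endpoint is defined as the VSS total score obtained at Visit 7 (Day 90) and at Visit 8 (Day 180"). It then describes the analysis in three steps.

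- The treatment effect "will be obtained at each of the two post-healing assessment time points, using analysis of variance (ANOVA) for the ITT population".
- A mixed model has treatment, visit and their interaction as fixed effects, with "subject as a random effect". The visit factor is "assessment time point (4 visits: Visits 5, 6, 7 and 8"). On the covariance: "The option of variance components will be used to define the covariance structure of the model".
- In addition, "model-based t-test comparisons between Santyl vs. Bacitracin will be performed for each of the 2 assessment time points".

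Section 7.1 adds a general rule: "All confidence intervals will be two-sided with 95% coverage". Neither section names a heterogeneous covariance, a robust standard error or a check of equal variance.

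The documents differ on when VSS is collected. Section 6.2.3 and Table 1 in Section 12 place it at Visits 7 and 8 only. Section 6.5.5 starts it once the wound has fully re-epithelialized, which can be earlier.

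**The concern.** A random subject effect plus a single residual variance implies the same total variance at every visit. The Day 90 and Day 180 comparisons then share an averaged standard error instead of each using its own. A visit with more spread than the average gets a standard error that is too small, and so too many false scar claims. A visit with less spread gets one that is too large, and so loses power.

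The documents give reasons why equal spread should not be taken for granted, though none proves it unequal:

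- The VSS items sum to a bounded score (3 + 2 + 5 + 3 = 13), so spread can shrink as scores approach 0.
- Section 6.2.3 times scar visits from Visit 1, and the Synopsis gives 1 to 6 weeks of treatment. Scar age would then run from 90 − 42 = 48 to 90 − 7 = 83 days at Visit 7 (1.7-fold), but from 138 to 173 days at Visit 8 (1.25-fold). Section 6.1 instead counts months from healing.
- Section 7.1.2 moves early-termination scores to the next scheduled visit, which mixes younger scars into a later slot.

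**Working it through.** **The plan's own figure.** Section 8 gives 40 per group, an effect size of 0.750, two-sided alpha of 0.05 and a two-sample t-test, with power of about 70%. The exact noncentral t gives 91.2%, so the stated figure is not reproduced. That is a separate matter and does not bear on the covariance, but 91.2% is the baseline for the power figures below.

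**Inputs.** 40 per arm, alpha 0.05 two-sided and effect size 0.750 come from Sections 7.1.2 and 8. The ratio of VSS SDs between visits is not in the documents and is assumed over a range.

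**Formula.** With complete data, the random-intercept model estimates the variance at every visit as the mean of the visit variances. Let k be the ratio of the model's standard error to the correct one at a given visit:

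k = √(mean variance / that visit's variance)

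True type I error = 2 × (1 − Φ(1.96 × k))

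**Visits 7 and 8 only.** Set the smaller SD to 1 and the larger to R. The mean variance is (1 + R²)/2.

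| R | mean variance | k, more variable | type I error | k, less variable | type I error |
|---|---|---|---|---|---|
| 1.0 | 1.000 | 1.000 | 5.0% | 1.000 | 5.0% |
| 1.1 | 1.105 | 0.956 | 6.1% | 1.051 | 3.9% |
| 1.2 | 1.220 | 0.920 | 7.1% | 1.105 | 3.0% |
| 1.3 | 1.345 | 0.892 | 8.0% | 1.160 | 2.3% |
| 1.5 | 1.625 | 0.850 | 9.6% | 1.275 | 1.2% |

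For example, at R = 1.3 and the more variable visit, k = √(1.345/1.69) = 0.892, and 2 × (1 − Φ(1.748)) = 8.0%.

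A simulation of the balanced model (REML, Satterthwaite degrees of freedom, within-subject correlation 0.6, 40,000 trials) gave 6.1%/3.9%, 7.2%/3.1%, 8.2%/2.4% and 9.5%/1.3% for R = 1.1, 1.2, 1.3 and 1.5. Using each visit's own variance gave 5.0% to 5.2% throughout.

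**Power at the less variable visit**, with the difference set at 0.750 of that visit's SD. The noncentrality is 0.750 × √(40/2) = 3.354, and the critical value t(0.975, 78) = 1.991 is multiplied by k. Power is 91% at R = 1.0, and 87%, 85% and 79% at R = 1.2, 1.3 and 1.5.

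**Four visits, as 7.1.2 lists.** Two illustrations, with SDs in the order Visits 5, 6, 7, 8 and complete data assumed:

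- SDs 1.3, 1.2, 1.0, 0.8: mean variance = (1.69 + 1.44 + 1.00 + 0.64)/4 = 1.1925. k = 1.092 at Day 90 and 1.365 at Day 180. Type I error is 3.2% and 0.7%, both conservative.
- SDs 0.5, 0.5, 1.0, 0.8: mean variance = (0.25 + 0.25 + 1.00 + 0.64)/4 = 0.535. k = 0.731 and 0.914. Type I error is 15.2% and 7.3%, both liberal.

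**The case against.** Four objections deserve weight.

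- **No unequal variance is shown.** The documents give no VSS SD at any visit. At an SD ratio of 1.1 the error rates are only 6.1% and 3.9%. This stands: the harm is conditional. A reader might infer that the 95% coverage promised in Section 7.1 certainly fails at both visits. The documents do not support that.
- **The direction is not fixed.** A reader might infer that the two visits' errors must run in opposite directions. That is certain only if Visits 7 and 8 alone supply VSS data. Sections 6.2.3 and 12 schedule it so, but the model in 7.1.2 names four visits and Section 6.5.5 allows earlier scores. The four-visit illustrations show both errors running the same way. This also stands, and it means the covariance cannot be settled apart from the list of visits.
- **A per-visit ANOVA may already be planned.** The first step in 7.1.2 can be read as a separate ANOVA at each time point. Each would use its own variance and be unaffected, and the t-tests, introduced as an addition, might then only be supportive. The text does not say whether the ANOVA is separate or is the mixed model that follows, so this limits the point without removing it.
- **The endpoint is secondary.** The analyses in 7.1.1 do not use this model. This stands and limits the weight of the point.

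**Conclusion.** The point holds in conditional form. As specified, the model imposes one variance on all included visits, the Day 90 and Day 180 t-tests inherit it, and no safeguard is stated.

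The two-visit figures rest on complete data, approximately normal scores and an assumed SD ratio. Over ratios of 1.1 to 1.5, type I error ranges from about 6% to 9.5% at one visit and from about 4% to just over 1% at the other. The power cost at the plan's own effect size is moderate: about 4 points at a ratio of 1.2 and 12 at 1.5. With four visits, neither the size nor the direction can be stated without knowing the early-visit spread.

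The case for changing the plan is not that an error has been demonstrated. A per-visit variance removes the dependence on an untested restriction and loses essentially nothing when the variances are equal.

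**What to change.** In Section 7.1.2:

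1. State which visits enter the VSS model, and reconcile this with Sections 6.2.3, 6.5.5 and Table 1 in Section 12. If VSS is collected only at Visits 7 and 8, limit the model to those two.
2. Replace the variance-components option with an unstructured within-subject covariance, fitted by REML with Satterthwaite degrees of freedom.
3. Take both visit-specific treatment differences and their 95% intervals from that model, and say whether the per-visit ANOVA is a separate analysis or this same one.

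The cost is a short edit, with no new data or subjects. For two visits the covariance goes from two parameters (subject and residual variance) to three (two variances and a covariance), which is one more. If four visits were kept, an unstructured covariance would need 4 × 5/2 = 10 parameters, so the visits should be settled first.

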7.1.3 Exploratory Efficacy

Burn wound status (closed or open) at each study visit will be compared between the two treatments, using ANOVA for the combination groups of the burn wound perfusion and Fitzpatrick skin type.

7.2 SAFETY

Safety variables include adverse events (AE). Adverse events will be coded using Medical Dictionary for Regulatory Activities (MedDRA) adverse event dictionary. Frequency of treatment emergent AE will be calculated for each body system, by preferred term, by treatment, for number of subjects and proportion reporting the event for the safety population. The severity of the AE and the relationship to study medication will be summarized for each body system and preferred term by treatment. Withdrawals, in general, and withdrawals due to AE will be summarized for each body system and preferred term by treatment.

8. SAMPLE SIZE JUSTIFICATION

A previous study of Santyl vs. white petrolatum in normal volunteers with dermatome wounds enrolled 28 subjects, each of whom served as their own control (paired wounds, treated differently). At 9 months follow-up, the Santyl treated wounds had lower total scores on the Vancouver Scar Scale, suggesting the efficacy of Santyl ointment, although the difference between Santyl and its petrolatum vehicle was not significant (P = 0.09, Wilcoxon signed-rank test).

The current study uses a parallel-group design and non-uniform injuries on different individuals, which are more likely to lead to a larger variance as compared to the previous study. The injuries are non-uniform and different in nature compared to the dermatome study. Assuming a moderate effect size of 0.750 for the present study, the sample size of 80 (40 per group) will yield a statistical power of approximately 70% to detect a difference between the two treatment groups at the significance level of 0.05 (2-sided). Based on a two-sample t-test, the current study is comparable in power to the described previous study.

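### Section 8: an effect size of 0.750 with 40 per group gives about 91% power, not the stated 70%, and the study cited there does not support 0.750

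*Combined protocol and SAP*

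**What the plan says.** Section 8 (Sample Size Justification) cites one study: Santyl against white petrolatum on dermatome wounds in 28 normal volunteers, each serving as their own control. Vancouver Scar Scale (VSS) totals at 9 months were lower with Santyl, but "the difference between Santyl and its petrolatum vehicle was not significant (P = 0.09, Wilcoxon signed-rank test").

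The section then notes that the present trial has parallel groups and non-uniform injuries, "which are more likely to lead to a larger variance as compared to the previous study". The planning assumption follows: "Assuming a moderate effect size of 0.750 for the present study". With 40 per group, the design "will yield a statistical power of approximately 70% to detect a difference between the two treatment groups" "at the significance level of 0.05 (2-sided"). The paragraph closes: "Based on a two-sample t-test, the current study is comparable in power to the described previous study".

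Section 8 gives no mean difference, standard deviation or within-pair correlation, and does not say which endpoint 0.750 refers to. VSS total at days 90 and 180 is the secondary endpoint (Section 7.1.2). The primary variables are healing at 3 weeks, time to healing and burn wound infection (Section 3).

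**The concern.** There are two separate problems.

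The first is internal. Effect size, group size, significance level and test together fix the power, and the four stated values do not lead to the stated 70%. A reader cannot tell whether the trial was planned on 0.750 or on something smaller.

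The second is the source of 0.750. The section moves from a non-significant paired result, through an expectation of larger variance, to an effect it calls moderate, with no step in between. For a given raw difference, larger variance makes the standardised effect smaller, so the section's own reasoning points away from 0.750. Correcting only the arithmetic would leave a reassuring 91% resting on an unsupported input.

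At stake is how a non-significant VSS comparison would be read. If the true effect is near the cited study's estimate, such a result is about as likely as not at best, and probable over most of the range below, even if Santyl improves scars.

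**Working it through.** **Inputs from Section 8:** d = 0.750; n = 40 per group; two-sided α = 0.05; two-sample t-test; stated power about 70%. Cited study: 28 pairs, P = 0.09, Wilcoxon signed-rank test.

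**Inputs not in the documents (assumed):** the within-pair correlation ρ, taken as 0, 0.25, 0.5 and 0.75. The Wilcoxon P is treated as if it came from a paired t-test. All 80 subjects are taken to contribute, in line with the Synopsis, which expects 80 to complete at 90 days.

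**Step 1. The plan's own figure.** The noncentrality is d × √(n/2) = 0.750 × √20 = 3.354, with 78 degrees of freedom and critical value 1.991. Power from the noncentral t is 91.2% (normal approximation 91.8%). The stated 70% is not reproduced.

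No obvious variant gives it either:
- one-sided 0.05: 95.4%
- α = 0.05/3: 81.5%
- α = 0.01: 76.0%
- rank-test efficiency of 0.955 or 0.864: 89.9% or 86.7%
- 20 per group: 63.7%

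At d = 0.750, 23 per group would already give 70%.

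**Step 2. What 40 per group can detect.** Solving the same expression for d gives 0.56 at 70% power, 0.63 at 80% and 0.73 at 90%.

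**Step 3. The cited study's effect.** Two-sided P = 0.09 with 27 degrees of freedom gives t = 1.758. The standardised paired difference is 1.758/√28 = 0.332 (0.320 if a normal deviate of 1.695 is used). Its approximate standard error is √(1/28 + 0.332²/56) = 0.194, so the 95% interval is 0.332 ± 1.96 × 0.194, or −0.05 to 0.71.

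**Step 4. Conversion to the parallel-group scale.** d = 0.332 × √(2(1 − ρ)):

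| Assumed ρ | Implied d | Approx. 95% interval | 0.750 ÷ d | 0.56 ÷ d | Power, 40 per group |
|---|---|---|---|---|---|
| 0 | 0.47 | −0.07 to 1.01 | 1.6 | 1.2 | 55% |
| 0.25 | 0.41 | −0.06 to 0.87 | 1.8 | 1.4 | 44% |
| 0.5 | 0.33 | −0.05 to 0.71 | 2.3 | 1.7 | 31% |
| 0.75 | 0.23 | −0.03 to 0.50 | 3.2 | 2.4 | 18% |

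These are before any of the extra variance that Section 8 expects.

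**Step 5. Comparable power.** For the same raw difference and standard deviation, the squared noncentrality is proportional to 28/(2(1 − ρ)) in the paired design and to 40/2 in the parallel design. They are equal when 40(1 − ρ) = 28, that is ρ = 0.3. Above 0.3 the new design is weaker; below it, slightly stronger. At its own observed effect the earlier study has about 40% power, and the new design's 18% to 55% lies on both sides of that.

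**The case against.** **The earlier study is weak evidence in either direction.** It used healthy volunteers, dermatome wounds, a petrolatum comparator and a 9-month assessment. This trial has burns, bacitracin and days 90 and 180. Section 2.1 also mentions burn studies reporting faster healing and less hypertrophic scarring. This stands: the implied effects should not be put in place of 0.750 as if they were the truth. It does not rescue 0.750, because neither Section 8 nor Section 2.1 gives a figure from which it could be derived.

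**A reader might infer that the earlier result rules out 0.750.** It does not. At ρ = 0 the interval reaches 1.01, and a true effect of 0.750 would give P of 0.09 or more about 15% of the time (7% at ρ = 0.25, 1.5% at ρ = 0.5). Only the higher correlations come close to excluding it.

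**A reader might infer that the claim "the current study is comparable in power to the described previous study" is false.** The documents do not show that. It would hold near ρ = 0.3, and the 40% for the earlier study is power at its observed effect, which only restates P = 0.09. The claim lacks support because the correlation it depends on is not given.

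**VSS is secondary.** Section 8 does not tie 0.750 to VSS, and nothing in the plan says that a non-significant scar result would be read as equal scars. This stands, and it limits the consequence to a risk of misreading. The mismatch between 0.750 and 70% does not depend on the endpoint.

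**Conclusion.** The point holds in two parts of different strength.

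The firm part needs no outside assumption: the stated inputs give about 91% power, not 70%, and 70% corresponds to about 0.56. The documents do not show which of the two was the planning value.

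The second part is conditional. For any non-negative within-pair correlation, the cited study's point estimate is at most about 0.47 on the parallel-group scale. Both candidate planning values exceed it: 0.750 by 1.6 to 3.2 times and 0.56 by 1.2 to 2.4 times for correlations from 0 to 0.75. Power at the implied effects is about 55% down to 18%, and lower still if the variance is larger as the plan expects. This rests on the assumed correlation, on reading a Wilcoxon P as a t statistic, and on a small study with a wide interval.

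The word *moderate* and the sentence on comparable power have no support in the section.

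**What to change.** In Section 8:
- Reconcile the two figures. Either state the effect detectable with 40 per group (about 0.56 at 70% power, 0.63 at 80%), or keep 0.750 and state about 91%.
- Name VSS total as the endpoint if that is what the calculation is for, and give the mean difference and standard deviation behind the effect size.
- Show power over the range implied by the earlier study, with the correlation assumption written out.
- Delete *moderate* and the sentence on comparable power.

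In Section 7.1.2, add that the VSS difference between treatments is reported with its 95% confidence interval.

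No patients, visits or assessments are added. The only cost is that the power shown at the effects implied by the cited study is less favourable than the present text suggests.

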2.2 RATIONALE

Outpatient management of partial thickness burns normally involves the application of an ointment, which may contain an antibiotic. Concerns about the promotion of antibiotic resistant staphylococci, combined with known risks of allergic hypersensitivity reactions to certain topical antibiotics, support the exploration of alternative treatments. Bacitracin ointment has been compared against white petrolatum in the management of post-procedural wounds among 922 patients with 1249 wounds (17). No significant difference was observed in infection rates (2% in the petrolatum group vs. 0.9% in the bacitracin group) or healing rates. No patients in the white petrolatum group developed allergic contact dermatitis compared with 4 patients (0.9%) in the bacitracin group. In a separate study of 142 patients, 147 Mohs micrographic surgery wounds on the ear were postoperatively treated with either gentamicin ointment or petrolatum. No significant differences were seen between treatments in the incidence of suppurative chondritis infections (4.76% in the gentamicin group; 6.67% in the petrolatum group), whereas there was a higher incidence of inflammatory chondritis in the gentamicin group (11.90% vs. 3.33% for petrolatum) (18). In the 1990s, the North American Contact Dermatitis Group (NACDG) listed bacitracin among the top 10 allergens, based on skin testing. Approximately 9% of bacitracin tests were positive.

. Bacitracin ointment is selected for this study because it is a standard treatment used by the Investigators, and is widely used in burn care. A significant cost difference exists between bacitracin and other ointments, such as Collagenase Santyl. The therapeutic intent for this study is to see if there is a cost reduction benefit as well as reduction in healing time for two standard of care treatment options for partial thickness burn wounds.

This trial does not include a rigorous evaluation of local infection, as quantitative bacteriology from biopsied tissue would be required, nor does it include a rigorous evaluation of hypersensitivity reactions, as de-challenge / re-challenge or measurement of specific humoral and cellular immune responses would be required. Instead, the appearance of the wound bed and periwound tissue will be evaluated, with

particular attention to the description of any rashes. Clinically diagnosed infections may be treated, but use of topical treatment will require that the subject exit the trial.

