7.1.1 Primary Efficacy

The primary objectives of the study include the proportion of subjects with the burn wound healed after 3 weeks of treatment, time (in weeks) to healing, and incidence of burn wound infection.,

Both the proportion of subjects with burn wound healed after 3 weeks of treatment and the time to heal between the two treatment groups will be analyzed using ANOVA. Also, the proportion of burn wounds healed at each of the 5 assessments (visit 2,3,4,5, and 6) between the two treatment groups will be analyzed through a mixed-effect ANOVA. The incidence of burn wound infection observed over the study will be compared between the two treatment groups, using a t-test.

The analysis of the primary efficacy evaluations will be performed for the ITT population.

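### Section 8 claims about 70% power, but its own inputs give 91.2%; it names no endpoint for the figure and attributes no power to any primary endpoint

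*Combined protocol and SAP*

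**What the plan says.** Section 8 (Sample Size Justification) first describes an earlier study in volunteers: 28 subjects with paired dermatome wounds, compared on the Vancouver Scar Scale (VSS) total score at 9 months, P = 0.09 by the Wilcoxon signed-rank test. It notes that the present parallel-group trial, with non-uniform injuries, is likely to have larger variance. It then gives the basis for the sample size:

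- Effect: "Assuming a moderate effect size of 0.750 for the present study".
- Size and power: "the sample size of 80 (40 per group) will yield a statistical power of approximately 70" percent.
- Test level: "at the significance level of 0.05 (2-sided").
- Test and comparison with the earlier study: "Based on a two-sample t-test, the current study is comparable in power to the described previous study".

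Section 8 does not say which outcome of the present trial the 0.750 refers to.

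The primary endpoints are set out in Section 7.1.1: "The primary objectives of the study include the proportion of subjects with the burn wound healed after 3 weeks of treatment", together with time to healing in weeks and the incidence of burn wound infection. The VSS is secondary under Section 7.1.2: "The secondary efficacy endpoint is defined as the VSS total score obtained at Visit 7 (Day 90) and at Visit 8 (Day 180"). Neither Section 7 nor the synopsis gives an assumed rate, standard deviation, power or detectable difference for a primary endpoint. The synopsis sends the reader to Section 11 for the justification, but Section 11 is the reference list.

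**The concern.** All the inputs to a standard power calculation are on the page, and they do not produce the stated result. A standardised effect of 0.750 with 40 per group is an easy target for a two-sample t-test, and 70% is far too low for it.

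This figure is the only quantitative reason given for enrolling 80 subjects. As written, a reader cannot tell whether the trial was planned around an effect of 0.75 or of about 0.56, and those are different claims about what it can show.

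The missing endpoint makes this worse. If the figure is simply corrected to 91%, it could be taken to cover the proportion healed or the infection rate, where 40 per group can detect only large differences. The statement that power is comparable to that of the earlier study cannot be checked either, because no effect size, standard deviation or power is given for that study.

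**Working it through.** **Inputs, all from Section 8:** standardised effect d = 0.750; n = 40 per group; two-sided α = 0.05; two-sample t-test. Equal allocation is confirmed in Section 6.1. The synopsis expects all 80 subjects to complete Day 90, so no attrition allowance enters.

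**Step 1. Try to reproduce the plan's figure.**

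Degrees of freedom = 2 × 40 − 2 = 78. Noncentrality = d × √(n/2) = 0.750 × √20 = 3.354. Power is the probability that a noncentral t with these parameters exceeds the two-sided critical value in absolute size.

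Result: **91.2%**. The normal approximation gives 91.8%. A two-group ANOVA with f = 0.750/2 = 0.375 also gives 91.2%. The stated figure of about 70% is not reproduced; the gap is 91.2 − 70 = 21.2 points.

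**Step 2. Work backwards from 70%.**

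- With n = 40 per group, 70% power corresponds to d = 0.562.
- With d = 0.750, 70% power needs 23 per group (70.1%; 22 per group gives 68.1%).

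**Step 3. Try other readings, keeping d = 0.750.**

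| Reading | Power |
|---|---|
| One-sided α = 0.05 | 95.4% |
| Rank test, relative efficiency 0.955 | 89.9% |
| Rank test, relative efficiency 0.864 (lower bound) | 86.7% |
| 10% attrition (36 per group) | 88.1% |
| 20% attrition (32 per group) | 84.0% |
| 30% attrition (28 per group) | 78.7% |
| α = 0.05/3 for three primary endpoints | 81.5% |
| α = 0.01 | 76.0% |
| 40 subjects in total (20 per group) | 63.7% |

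None gives 70%. Getting there takes an input the plan does not state: α near 0.005 (67.8%), attrition just over 40% (40% gives 72.0%), or a standard deviation inflated by 0.750/0.562 = 1.33.

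**Step 4. What 40 per group means for the two binary primary endpoints.**

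The documents give no healing rates, so the rates below are assumptions. Power is by exact binomial enumeration, two-sided 0.05. The planned ANOVA on a healed/not-healed outcome and the uncorrected chi-square test reject for exactly the same tables at 40 per arm, so they share a column.

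| Healed at Day 21 (assumed) | ANOVA or chi-square | Fisher's exact |
|---|---|---|
| 50% vs 80% | 82% | 75% |
| 60% vs 87% | 80% | 73% |
| 70% vs 93% | 80% | 71% |
| 60% vs 75% | 29% | 22% |

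For infection, the only bacitracin rate in the documents is in Section 2.2: "No significant difference was observed in infection rates (2% in the petrolatum group vs. 0.9% in the bacitracin group) or healing rates". Those were post-procedural wounds, so the figure only illustrates the case for burns. Starting from 0.9%, the planned t-test reaches 80% power only if the other arm has about 16% infections (about 21% with Fisher's exact test). If the bacitracin rate is assumed to be 5%, the other arm must reach about 26% (t-test).

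**The case against.** The strongest reply is that Section 8 warns of larger variance than in the earlier study. If 0.750 was the effect before that allowance and the standard deviation was then inflated by 1.33, the effect becomes about 0.56 and 70% is right. This is possible, but the text does not say it. It attaches 0.750 to the present study, after the remark about variance, and a standardised effect already includes the variance. Even on this reading the stated effect size is the wrong figure, so the contradiction remains.

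A second point is that the error runs in the safe direction. If 0.750 was intended, power is understated and no subject numbers need to change. That is true and limits the harm, but it does not make the sentence correct.

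A third is that, with no endpoint named, the calculation might have been meant for time to healing. That is a primary endpoint analysed by ANOVA, which with two groups is equivalent to the t-test. This cannot be excluded. The VSS is the likelier reading because it is the only outcome Section 8 mentions, but that is an inference. What can be said firmly is that no power is attributed to any primary endpoint. The healing and infection figures above illustrate scale and are not needed to show the error.

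**Conclusion.** The concern holds. On Section 8's own inputs the power is 91.2%, not about 70%. This follows from stated figures alone and needs no outside assumption. Either the power or one of its inputs is misstated, and nothing elsewhere in the documents settles which. This does not show that 80 subjects are too few for an effect of 0.750.

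The endpoint to which the calculation applies is not named, and no primary endpoint has a stated power or detectable difference. On assumed healing rates, 40 per group gives about 80% power only for differences of roughly 23 to 30 percentage points (70% vs 93% up to 50% vs 80%), and 29% power for 60% vs 75%. Those figures depend on the assumed rates and on the test used. The claim of comparable power with the earlier study is unsupported as it stands. Because the misstated figure is the sole justification for the sample size, it must be corrected.

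**What to change.** In Section 8:

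1. The sponsor confirms which input was intended and restates the sentence, for example as 91% power for an effect size of 0.750, or 70% power for an effect size of 0.56, each with 40 per group, two-sided 0.05 and a two-sample t-test.
2. Name the endpoint and time point to which the effect size applies. If it is the VSS, say that the calculation rests on a secondary endpoint.
3. Add the difference in proportion healed at Day 21 that 40 per group can detect, with the test and the assumed control rate. State that the restated power does not extend to healing or infection unless it is calculated for them separately.
4. Give the basis for the comparison with the earlier study, or delete it.

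The synopsis cross-reference to Section 11 can be corrected to Section 8 at the same time.

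The cost is wording only; enrolment and analysis need not change. The detectable healing difference will look less favourable than the restated power figure.
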